1.0 Study Summary

Study Title	Bacteriostatic Normal Saline versus lidocaine for intradermal anesthesia during lumbar medial branch blocks
Study Design	Randomized, double blinded, comparative study
Primary Objective	To determine if intradermal administration of bacteriostatic normal saline is less painful than 1% lidocaine plain
Secondary Objective(s)	To determine if intradermal bacteriostatic normal saline provides a similar level of skin anesthesia compared to 1% lidocaine plain
Research Intervention(s)/Interactions	Creation of skin wheals during a chronic pain procedure, specifically lumbar medial branch blocks, and assessment of pain scores
Study Population	Chronic pain patients
Sample Size	40
Study Duration for individual participants	30 minutes
Study Specific Abbreviations/ Definitions	BNS – Bacteriostatic normal saline MBB – Medial branch block NRS – Numeric rating scale
Funding Source (if any)	Internal funds from the Pain Medicine Fellowship, Department of Anesthesiology, Emory School of Medicine

2.0 Objectives

2.1 The aim of this study is to test whether intradermal bacteriostatic normal saline reduces procedure-related pain compared to lidocaine 1% plain in subjects with chronic axial low back pain. Specifically, this study will compare the pain associated with creation of a skin wheal and the resulting level of anesthesia between the two medications during a lumbar medial branch block (MBB).

- Objective #1 – To compare the pain experienced with creation of a skin wheal with bacteriostatic normal saline versus 1% lidocaine plain.
- Objective #2 – To compare the pain experienced when placing a needle through the skin wheal created with bacteriostatic normal saline versus 1% lidocaine plain.

2.2 Hypotheses

- Hypothesis #1 – *Injection of bacteriostatic normal saline (BNS) for skin wheal will show lower patient-reported pain scores on injection than that of 1% lidocaine.*
- Hypothesis #2 – *Injection of BNS for skin wheal anesthesia is non-inferior to that of the injection of the standard of care, 1% lidocaine, during medial branch block procedure.*

3.0 Background

3.1 Interventional pain procedures are performed to aid in the diagnosis and treatment of chronic pain. Like any invasive procedure, they carry a risk of procedure-related pain that may affect the patient in a negative way. Temporary consequences include the heightened pain itself, anxiety, premature abortion of the procedure, increased heart rate and blood pressure, and vasovagal reactions. Longer-term issues include aversion and/or anxiety to future procedures. These procedures are performed in patients with chronic pain and they may experience a heightened level of pain compared to patients without chronic pain. Also, it is often the case that creation of a skin wheal with local anesthetic is the most painful part of the procedure. [1] Some clinicians have resorted to moderate sedation and even general anesthesia to help reduce procedure-related pain; however, recent guidelines have advised against this practice since it has been associated with negative outcomes. [2]

3.2 Lumbar medial branch blocks are a specific interventional pain procedure used to determine if chronic axial low back pain is originating from facet, or zygapophyseal joints. Facet joints are innervated by medial branch nerves which arise from the dorsal ramus branch of spinal nerve roots. The procedure entails blocking the corresponding medial branch nerves for a given facet joint with a small amount of local anesthetic. If the patient has significant pain relief, there is a high likelihood that their pain is arising from the targeted joints. [3,4] Because the procedure is diagnostic in nature, limiting the amount of local anesthetic injected is of paramount importance. If other possible pain-generating structures are blocked with local anesthetic, it will make it impossible to determine which structure is causing pain. Therefore, typically only a skin wheal is created to limit pain on needle insertion besides the local anesthetic injected at the medial branch nerve. It is also important to minimize intravenous sedation for the same reason. In addition to the consequences of increased procedure-related pain stated above, increased pain during a medial branch block has been shown to increase false-negative results. [5]

4.0 Study Endpoints *

- 4.1 The primary study endpoint is the improvement in procedure-related discomfort during a lumbar MBB.
- 4.2 There are no safety-related endpoints.

5.0 Study Intervention/Investigational Agent

- 5.1 The study intervention is the creation of a skin wheal (intradermal injection) with BNS and 1% lidocaine plain.
- 5.2 Drug/Device Handling: The storage, handling, and blinding of the medications will be performed by Grady Pharmacy using their established protocol. The administration of the medications (i.e. intradermal injection) will be performed by the principal investigator (PI).

6.0 Procedures Involved*

- 6.1 An individual's participation will occur during a lumbar medial branch block procedure. All subjects will have qualified for a lumbar medial branch block due to axial low back pain with lumbar spondylosis as the primary diagnosis. All subjects would have received lumbar medial branch blocks during their normal clinical course whether or not they choose to participate in this study
- 6.2 This study will focus solely on skin wheal creation and resulting skin anesthesia with lidocaine 1% and bacteriostatic saline. The lumbar medial branch block procedure typically requires two or more skin wheal injections prior to placement of the spinal needle that ultimately delivers the block. Subjects will serve as their own control. The first two skin wheals will be utilized for the study and the medications will be randomized with both the subject and investigator blinded to the medication used for each one. The first two skin wheals and placement of the first two spinal needles through these skin wheals will be performed by the principal investigator to promote consistency.
- 6.3 Using a standardized script, the participant will be informed that the medication will be administered. The skin wheal will be created by injecting the medication intra-dermally with a 26 gauge needle. The patient will be asked to rate on the numerical rating scale (NRS) the pain experienced with creation of the skin wheal. This process will then be repeated with the second skin wheal. Next, the first needle for the block will be inserted through the first skin wheal. The patient will again be asked to rate, on the NRS, the pain of needle insertion. For this procedure, a 22 gauge Quincke spinal needle will be used with a length of either 3.5 or 5 inches. This process will again be repeated by inserting the second needle through the second skin wheal.
- 6.4 At this point, the individual's participation in the research study is complete and the lumbar medial branch block will be continued as usual with any subsequent skin wheals created with 1% lidocaine plain (standard of care, not study related). The remainder of the medial branch block (after the conclusion of the individual's participation in the study) may be performed by the pain fellow or the principal investigator (attending).
- 6.5 Basic demographics (age, gender) and baseline pain score will be collected directly from the participant by the investigator before the intervention. During and after the intervention, the levels (L2, L3, L4, etc) and laterality injected and pain scores from the intervention will be collected directly from the subject by the investigator. No identifiable PHI will be collected or stored.

7.0 Data and Specimen Banking* N/A

N/A

8.0 Sharing of Results with Participants*

8.1 This study does not involve any testing (diagnostic, genetic, imaging, etc.) that may generate potentially shareable results.

9.0 Study Timelines*

9.1 The duration of an individual participant's participation is approximately thirty (30) minutes. We anticipate the duration of enrollment to be approximately four (4) months assuming an average of three to four (3-4) lumbar medial branch blocks scheduled per week based on past procedure volumes. We anticipate an additional one (1) month for data analysis.

10.0 Inclusion and Exclusion Criteria*

10.1 When the patient arrives for the scheduled lumbar medial branch block, the subject will be consented for the procedure. After consenting for the procedure, one of the investigators will screen the patient for eligibility in the study.

10.2 Inclusion criteria – any patient scheduled for an initial lumbar medial branch block

10.3 Exclusion criteria

- Allergy to local anesthetics
- Fibromyalgia
- Inability to provide informed consent in English

10.4 We will also exclude the following special populations:

- Adults unable to consent
- Individuals who are not yet adults (infants, children, teenagers)
- Pregnant women
- Prisoners

10.5 Community Participation: N/A

11.0 Vulnerable Populations* N/A

N/A

12.0 Local Number of Participants

PROTOCOL TITLE: Bacteriostatic Normal Saline versus lidocaine for intradermal anesthesia during lumbar medial branch block.

12.1 Based on the power analysis, the total number of participants will be forty (40). We will plan to screen fifty (50) subjects assuming some may not consent to the study or may be excluded based on the exclusion criteria. Since the lumbar medial branch block is rarely performed in patients with a local anesthetic allergy or fibromyalgia, we expect the excluded subjects to be quite low.

13.0 Recruitment Methods

- 13.1 Potential participants will be asked to participate after he/she has consented to the lumbar medial branch block procedure.
- 13.2 Participants come from the patient population at the Grady Pain Clinic.
- 13.3 Any patient that is planning to undergo a lumbar medial branch block is a potential participant.
- 13.4 There will not be any recruitment materials since only patients undergoing lumbar medial branch blocks are potential participants which is a small subset of the patient population at the Grady Pain Clinic.
- 13.5 There will be no payments for participation or reimbursement for expenses/travel since the overall procedure is part of the subject's usual medical care

14.0 Withdrawal of Participants*

- 14.1 If a participant chooses to not undergo the procedure after consenting but before creation of the first skin wheal, the participant will be withdrawn from the research.
- 14.2 If a participant chooses to abort the procedure after creating of the first skin wheal, the procedure will be immediately stopped. While this participant will not count to our goal of forty (40) participants, the data will be analyzed to identify if there is a pattern regarding subjects that abort the procedure (i.e. is the creation of the skin wheal too painful or does not supply an adequate level of anesthesia for the spinal needle).

15.0 Risks to Participants*

- 15.1 It is foreseeable that the participant may experience pain/discomfort with the creation of the skin wheal or placement of the spinal needle through the skin wheal created by BNS. Since creation of a skin wheal with 1% lidocaine plain is standard of care, pain/discomfort occurring from this is unfortunately expected and unavoidable and the basis of performing this research to identify better options. The probability that the participant will experience significantly more pain/discomfort from BNS is very low given the results of prior studies. Any pain/discomfort experienced related to the skin wheal will be of a very short duration (seconds).

15.2 The participant may experience an allergic reaction to the medications however this is also extremely low.

15.3 Given the short duration of the medications administered, there are no risks to an embryo or fetus should the subject become pregnant after the study. Subjects currently pregnant are excluded.

16.0 Potential Benefits to Participants*

16.1 A potential benefit includes less pain with injection of BNS; however, the magnitude of this benefit is low since only one skin wheal will be created with BNS. The rest will be created with 1% lidocaine plain.

17.0 Data Management* and Confidentiality

17.1 Data will be analyzed using SAS 9.4 (Cary, NC) by the Anesthesiology Department's Biostatistician. For the first hypothesis, a General Linear Model will be applied, which is equivalent to a modified matched-pairs t-test, but allows for inclusion of potential confounders, such as the injection order. If assumptions of the General Linear Model are not met, e.g. the data are too leptokurtic or too positively skewed, then another statistical test such as Ordinal Logistic Regression will be used instead. For the second hypothesis, a non-inferiority test will be conducted, calculating delta as the maximum value for the 90% confidence interval, with an effect size of 0.24, an alpha set at 0.1, and a standard deviation of the difference determined from the sample data.

17.2 Power analysis was conducted with G*Power 3.1.9.4 (Düsseldorf, Germany). [20] A two-tailed a priori difference between two dependent means (matched pairs) was conducted. Alpha (Type I error) was set at 0.05 and power was set at 0.80. An effect size was set at 0.46, which is the mean effect size of a meta-analysis, [15] and is lower than the effect size of 0.52 calculated for a similar study. [11] This yielded a minimum required sample size of N=40.

17.3 Guidelines provided by the Grady/Emory Data and Safety Monitoring Board will be followed for this study data. Envelopes with random assignment of subjects to treatment arms will be in a locked filing folder and stored at the Grady Pain clinic office. No names, MRNs, or other personal identifiers will be used for the subjects - they will be given a random number identifier. Data results of subject's VAS scores will be immediately loaded to an encrypted and password protected Excel file and/or RedCap. The principal and secondary investigators will have access to the locked office/filing folder. If any reportable events are identified, they will be reported to the IRB as required by regulations. All study records will be reviewed at least annually.

17.4 Data results of subject's NRS scores will be immediately loaded to an encrypted and password protected Excel file and/or RedCap. The data will include the randomly assigned number identifier of the subject and the result of their NRS score. Data will be stored for 3 years. Only [name]

PROTOCOL TITLE: Bacteriostatic Normal Saline versus lidocaine for intradermal anesthesia during lumbar medial branch block.

[name], MD (PI) will have access to the data, and he is responsible for the receipt and transmission of the data.

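### Section 17.1 fixes no usable non-inferiority margin or decision rule for Hypothesis 2, and the same 40 pairs can give opposite verdicts depending on how the sentence is read

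*Combined protocol and SAP*

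**What the plan says.** Section 2.2 states the second hypothesis without a margin: "Injection of BNS for skin wheal anesthesia is non-inferior to that of the injection of the standard of care, 1% lidocaine". The matching objective in 2.1 is "To compare the pain experienced when placing a needle through the skin wheal created with bacteriostatic normal saline versus 1% lidocaine plain". The outcome comes from 6.3: "The patient will again be asked to rate, on the NRS, the pain of needle insertion". The comparison is within patient, since 6.2 says "Subjects will serve as their own control".

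The whole specification of the test is one sentence in 17.1. It announces a non-inferiority test and defines it by "calculating delta as the maximum value for the 90% confidence interval, with an effect size of 0.24, an alpha set at 0.1". The spread that enters the calculation is not a planning value; the same sentence takes it from the trial itself, as "a standard deviation of the difference determined from the sample data". No other section gives a margin, a source for 0.24, or a rule for declaring non-inferiority.

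The power analysis in 17.2 concerns a different test: "A two-tailed a priori difference between two dependent means (matched pairs) was conducted", with effect size 0.46, alpha 0.05 and power 0.80, giving N=40. Sources are cited there for 0.46 and for the comparison value 0.52. None is given for 0.24.

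**The concern.** A non-inferiority test needs a margin set in advance, an interval for a named quantity, and a rule linking the two. Section 17.1 makes delta itself a confidence limit, does not name the quantity, and states no rule. The 0.24 is called an effect size, so it could be the margin, the centre of an interval, an assumed true difference, or something else.

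Hypothesis 2 is secondary, but it asks whether BNS numbs the skin well enough to replace the standard of care. A less painful wheal does not answer that. If the sentence supports several tests, the choice among them can be made after the results are known. Section 18.1 has the fellows and the principal investigator review efficacy data every quarter and does not say that this review is blinded, so nothing in the plan rules that out.

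**Working it through.** **Inputs.** N=40 pairs (12.1, 17.2); effect size 0.24, 90% interval, alpha 0.1 and SD from the sample (17.1); effect size 0.46, two-tailed alpha 0.05 and power 0.80 (17.2). The documents give no SD of the paired difference, so results are in SD units, with 1.5, 2 and 3 NRS points as assumed values. Paired differences are taken as normal. d is the mean of BNS minus lidocaine divided by the SD; positive means BNS is worse.

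**The plan's own figure.** For a paired two-sided t-test with effect size 0.46, noncentral-t power is 0.799 at n=39 and 0.810 at n=40. The stated N=40 reproduces for Hypothesis 1.

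**Half-widths at N=40 (39 df).**
- Two-sided 90% interval (one-sided 0.05): 1.685/√40 = 0.2664 SD.
- One-sided 0.10: 1.304/√40 = 0.2061 SD.

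Neither equals 0.24, so the plan's N and alpha do not explain that number.

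**Three illustrative readings.** Other readings are possible.
1. Delta is the upper 90% limit around 0.24: 0.24 + 0.2664 = 0.5064 sample SDs. Non-inferiority is declared if observed d < 0.5064 − 0.2664 = 0.24.
2. Delta is 0.24 × sample SD. With the 90% interval, the claim needs observed d < 0.24 − 0.2664 = −0.0264, so BNS must look slightly better. At one-sided 0.10 it needs d < 0.24 − 0.2061 = +0.0339.
3. Delta is the upper limit of the trial's own 90% interval, "calculating delta as the maximum value for the 90% confidence interval" taken literally. The limit is compared with itself: always non-inferior if equality counts, never if it does not. The 0.24 has no role.

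**Probability of declaring non-inferiority** (noncentral t):

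| True d | 0.24 × SD, 90% CI | 0.24 × SD, one-sided 0.10 | 0.506 SD, 90% CI | Opposite verdicts, first vs last |
|---|---|---|---|---|
| −0.1 | 0.680 | 0.801 | 0.983 | 0.303 |
| 0 | 0.434 | 0.584 | 0.931 | 0.497 |
| +0.1 | 0.212 | 0.337 | 0.806 | 0.594 |

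The last column is P(−0.0264 < observed d < 0.24). A simulation of 200,000 trials at d=0 gave 0.432, 0.582, 0.931 and 0.499.

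**Type I error, each at its own margin.** 0.046 (90% CI) and 0.096 (one-sided 0.10) at d=0.24; 0.047 at d=0.506. If BNS is truly 0.24 SD worse, the 0.24 rule with the 90% CI passes it in 4.6% of trials and the 0.506 rule in about 50%.

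**In NRS points.** At 39 df the sample SD has a 95% range of 0.779 to 1.221 times the true SD, and the margin moves with it.

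| Assumed SD | 0.24 SD margin (95% range) | 0.506 SD margin (95% range) | Observed differences giving opposite verdicts |
|---|---|---|---|
| 1.5 | 0.36 (0.28–0.44) | 0.76 (0.59–0.93) | −0.04 to 0.36 |
| 2 | 0.48 (0.37–0.59) | 1.01 (0.79–1.24) | −0.05 to 0.48 |
| 3 | 0.72 (0.56–0.88) | 1.52 (1.18–1.85) | −0.08 to 0.72 |

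**Power if 0.24 SD were a fixed margin.** At N=40 and true d=0: 0.439 (one-sided 0.05) or 0.587 (0.10). At true d=0.1: 0.219 or 0.343. Pairs needed for 80% power: 109 or 80 at d=0; 317 or 231 at d=0.1.

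**The case against.** The best defence is that 0.24 is a standardised margin chosen in advance. The test would then be valid, with type I error close to nominal even though the SD is estimated, and a margin that moves in NRS points is a feature of any standardised margin. That is correct, and using the sample SD is not in itself the fault. But the sentence calls 0.24 an effect size and defines delta as something else, and even on this reading the number has no justification.

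The circular reading leaves 0.24 idle and is unlikely to be what was intended. That is fair, but it is what the words say if the interval is taken to be the trial's own.

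A 90% interval and alpha 0.1 agree if alpha is two-sided, so the one-sided 0.10 column deserves less weight. That also stands, although the text does not state sidedness.

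The 30%, 50% and 59% compare the strictest and most lenient workable rules. Setting the one-sided 0.10 rule against the 0.506 SD rule narrows the disagreement to 0.983 − 0.801 = 18%, 0.931 − 0.584 = 35% and 0.806 − 0.337 = 47%. That is smaller but still large. The 0.506 is derived here and is not printed in the plan.

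Finally, a secondary hypothesis need not be powered, and 17.2 does not claim that it is. The missing power figure is a reporting gap and not a contradiction.

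**Conclusion.** The concern holds. The Hypothesis 2 rule is wrong as written: circular if taken literally, and otherwise at least two different tests with no means of choosing between them. With truly equal agents and 40 pairs, the chance of a non-inferiority claim runs from 43% to 93% across the two workable readings at the 90% interval. They conflict whenever the observed mean difference lies between −0.026 and +0.24 sample SDs.

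That the rule is undefined follows from the text alone. The percentages assume normal paired differences, which is an approximation for a bounded, discrete pain scale, and the NRS-point figures rest on assumed SDs. Because the hypothesis is secondary and Hypothesis 1 and N=40 are untouched, this should be fixed but does not threaten the primary result.

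**What to change.** Replace the sentence in 17.1 before any unblinded data are seen:

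- Remove the definition of delta as the maximum of a confidence interval.
- Fix a margin that the sponsor justifies and that does not depend on the trial's data, preferably in NRS points. If a standardised margin is kept, give the source of the number and the SD it refers to.
- State the rule: non-inferiority is declared only if the upper limit of the two-sided 90% interval (one-sided alpha 0.05) for mean BNS minus lidocaine needle-insertion NRS lies below the margin.
- In 17.2, say that N=40 and power 0.80 apply to Hypothesis 1 only, and give the power for Hypothesis 2 at the chosen margin with its assumed true difference.
- If no margin can be justified, report the interval and make no non-inferiority claim.

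The cost is a few sentences, with no extra patients and no change to the primary test. The stated power for Hypothesis 2 may turn out low: about 0.43 to 0.44 at one-sided 0.05 if 0.24 SD is kept and the agents are truly equal, and about 0.21 to 0.22 if BNS is 0.1 SD worse.

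### The Hypothesis 2 interval names no sequence term, so any needle-position effect would inflate its SD; adding the term is a minor, free gain in precision

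*Combined protocol and SAP*

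**What the plan says.** Section 17.1 of the combined protocol and SAP handles the two hypotheses differently. Hypothesis 1 (pain of making the wheal) gets a general linear model, chosen partly because it "allows for inclusion of potential confounders, such as the injection order". Hypothesis 2 (pain of the spinal needle through the wheal) gets another method: "a non-inferiority test will be conducted, calculating delta as the maximum value for the 90% confidence interval". Three inputs are listed for it. Two are numbers, a standardised effect of 0.24 and a 10% alpha level; the third is "a standard deviation of the difference determined from the sample data". No model, covariate or order term is named for this second analysis, in 17.1 or elsewhere.

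Section 6.2 makes the comparison within patient ("Subjects will serve as their own control") and says that "the medications will be randomized with both the subject and investigator blinded to the medication used for each one". It does not say whether the two drug orders are balanced. Section 6.3 has both wheals made and rated first. "Next, the first needle for the block will be inserted through the first skin wheal", and once that insertion has been rated, "This process will again be repeated by inserting the second needle through the second skin wheal". Needle position therefore follows wheal position, and which drug sits in which position varies between patients by randomisation.

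**The concern.** The two insertions differ systematically. The second always comes just after another spinal needle has been inserted and rated; the first never does. If this changes the reported pain, the change enters the BNS-minus-lidocaine difference with one sign in patients given BNS first and the opposite sign in those given it second. An ordinary SD of the differences counts that as noise, although sequence is known and could be fitted. The plan itself names injection order as a possible confounder for Hypothesis 1, so its absence from the companion analysis of the same randomised pairs stands out. A non-inferiority decision depends on the upper confidence limit, and section 17.2 sizes the trial for a difference test only, so Hypothesis 2 has little precision to spare.

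**Working it through.** **Inputs.** N = 40 pairs (17.2); 90% interval, effect size 0.24 and alpha 0.1 for Hypothesis 2 (17.1), with alpha read as two-sided, so 0.05 on the side that matters. The documents give neither an SD nor a position effect. All results are therefore in units of the residual SD, over an assumed range of position effects.

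**1. The plan's own figure.** A two-sided paired t-test with effect size 0.46 and alpha 0.05 first reaches 80% power at N = 40 (exact power 0.810). The stated N reproduces.

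**2. Model.** For patient i, D_i = τ + s_i·g + e_i. D is the BNS-minus-lidocaine needle score, s = +1 if BNS is in position 2 and −1 if in position 1, g is the position effect and SD(e) = 1. With 20 patients per sequence:

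- SD of the differences without a sequence term: √(1 + g²·40/39); with the term: 1.
- 90% half-width without the term: t(0.95, 39)·SD/√40, where t = 1.6849.
- 90% half-width with the term: t(0.95, 38)/√40 = 1.6860/6.3246 = 0.2666.

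Example, g = 0.5: SD = √(1 + 0.25 × 1.0256) = 1.1209; half-width = 1.6849 × 1.1209/6.3246 = 0.2986; ratio = 0.2986/0.2666 = 1.12; equivalent N = 40/1.12² ≈ 32.

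| g (assumed) | SD without term | Half-width without | Half-width with | Ratio | Equivalent N |
|---|---|---|---|---|---|
| 0 | 1.000 | 0.266 | 0.267 | 1.00 | 40 |
| 0.25 | 1.032 | 0.275 | 0.267 | 1.03 | 38 |
| 0.5 | 1.121 | 0.299 | 0.267 | 1.12 | 32 |
| 1.0 | 1.423 | 0.379 | 0.267 | 1.42 | 20 |

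**3. Coverage** (simulation, 100,000 trials per setting). With 20:20 sequences the unadjusted 90% interval covers 91.2%, 93.5% and 98.0% for g = 0.25, 0.5 and 1.0. Under simple randomisation it covers about 90% throughout, because imbalance between sequences then makes the estimate itself more variable: its SD is 0.163, 0.176 and 0.224, against 0.158 at g = 0.

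**4. Chance of concluding non-inferiority when the drugs are truly equal** (20:20 sequences). Section 17.1 does not make the margin clear, so several readings are shown. The 0.5 margin is an assumption.

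| Margin and interval | g = 0 | 0.25 | 0.5 | 1.0 |
|---|---|---|---|---|
| Fixed, 0.24 residual SD; no term | 44% | 42% | 36% | 20% |
| Same margin; with term | 44% | 44% | 44% | 44% |
| Fixed, 0.5 residual SD; no term | 93% | 92% | 90% | 77% |
| Same margin; with term | 93% | 93% | 93% | 93% |
| 0.24 × unadjusted sample SD; no term | 43% | 43% | 43% | 41% |
| 0.24 × unadjusted sample SD; with term | 43% | 45% | 51% | 68% |

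In the fifth row, margin and interval widen together, so power hardly changes. The margin in residual-SD units, however, grows from 0.24 to 0.24 × 1.423 = 0.34 at g = 1. The last row mixes an adjusted interval with a margin scaled by the unadjusted SD; its apparent gain comes partly from that looser margin.

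**The case against.** The case for leaving the plan alone has several parts.

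- *The SD phrase may not set the interval.* It stands beside the standardised effect size and could be there to turn 0.24 into NRS points. Section 17.1 is also silent on order for Hypothesis 2; it does not exclude it. Both points stand. The unadjusted interval is the plain reading, supported by the contrast with Hypothesis 1, but it is a reading.
- *No position effect is documented.* Section 6.3 shows that the insertions differ in what precedes them, not that pain differs. At g = 0.25 the cost is 3% of width, and the larger figures need a nuisance effect above the 0.46 used to size the trial. This stands, and it limits the point to a minor one.
- *The unadjusted paired analysis is valid.* This is true. A reader might infer that the estimate is biased or that false non-inferiority claims become more likely. Neither follows: randomised order protects the estimate, and where coverage departs from nominal it is conservative. Nor can over-coverage be asserted, because it needs balanced sequences, which the documents do not state.
- *The power loss depends on the margin.* This is correct. It would be wrong to say that power suffers whatever margin is chosen, as the fifth row of the second table shows.

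What survives is that a known design factor is left out of one of two parallel analyses, and including it costs almost nothing.

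**Conclusion.** The point holds as a matter of precision. If the two needle positions differ in pain, the Hypothesis 2 interval as described is wider than it need be: by about 3%, 12% or 42% for position effects of 0.25, 0.5 or 1.0 residual SD, and not at all if there is no effect. This rests on the plain reading of 17.1, on N = 40 with 20:20 sequences for the exact figures, and on an assumed range of effects. A margin fixed in NRS points turns the extra width into lost power; a margin scaled by the same sample SD instead turns it into a looser margin.

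A reader might also infer that the sequence term would rescue the non-inferiority test. It would not. If the margin is 0.24 SD, the half-width of 0.266 already exceeds it with no position effect, and power with the term is about 44%. That is a separate problem. This one is a free improvement, minor, for a secondary objective.

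**What to change.** In 17.1, state that the Hypothesis 2 90% interval comes from a linear model of the within-patient BNS-minus-lidocaine needle NRS difference. Include a sequence term (BNS first or lidocaine first) coded ±1, so that the intercept is the drug effect averaged over the two positions, and use the residual SD with its degrees of freedom. Keep the unadjusted paired interval as a sensitivity analysis.

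State separately how the margin is set, because the phrase being replaced may be what scales 0.24. Preferably prespecify it in NRS points, not scaled by the trial's own SD. If an SD does scale it, say which one.

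The cost is a short edit and one degree of freedom (t moves from 1.6849 to 1.6860, under 0.1%). Unequal sequences add a little: an assumed 24:16 split gives variance ¼(1/24 + 1/16) = 0.0260 against 1/40 = 0.0250, about 2% on the standard error. No new data are needed, since sequence must be known to label each score by drug. Making the change before unblinding also removes any later choice between adjusted and unadjusted results.
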